6.2. POPULATION DESCRIPTION BEFORE MATCHING

The study population and exposure groups identified in each of the study countries will be described at index date using the following baseline characteristics:

- Demographics and other baseline characteristics at index date Table 11.
- Diabetic complications Table 12 (status at index date).
- Non-diabetic concomitant disease Table 13 (status at index date).
- Diabetic concomitant medication use Table 14 (status at index date).
- Non-diabetic concomitant medication use Table 15 (status at index date).

All continuous variables will be described using standard statistical measures, i.e. range, mean, standard deviation, median, first and third quartile. All categorical variables will be summarized with absolute and relative frequencies.

A summary table will be presented for each of the study countries separately (2 tables). A table template is given in Table 17.

6.3. METHODS ADDRESSING BIAS

Potential biases will be addressed as follows:

- Selection bias and immortal time bias is addressed thru the study design. It include a new user cohort design, a selection of comparator drugs with the same indication and prescribed to patients with potentially similar T2D disease severity, and a definition of exposure and study entry based on information before or at index date.
- Channeling bias is addressed by using propensity score matching to construct balanced exposure groups. In addition, the year of the index date (date of first prescription of the study group) is used as an exact matching criteria.
- Bias due to definitions of exposure, definition of follow-up times and other relevant covariates will be addressed through sensitivity analyses.

Proprietary confidential information © 2024 Boehringer Ingelheim International GmbH or one or more of its affiliated companies

- Diagnostic bias will be evaluated and addressed in sensitivity analyses through consideration of the frequency of urine dipstick testing (as captured through albuminuria tests) and stage of cancer at the time of diagnosis (as more early-stage cancers in one group would be suggestive of diagnostic bias).

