Study size:	
The study size will be driven by the uptake of empagliflozin and DPP-4 inhibitors for the treatment of T2D to improve glycaemic control in adults in the UK, Sweden, and Finland. Study-size and power computations were carried out for the meta-analysis of the primary outcomes. Originally, it was expected that by the end of 2019, approximately 18,000 empagliflozin-treated patients will accumulate in the CPRD and Swedish databases. However, based on the conservative estimates from the third monitoring report (2019), the expected sample size was higher than anticipated with approximately 25,000 empagliflozin initiators eligible for inclusion in the study. Further, additional 38,000 patients were expected by the end of 2020 with the inclusion of Finnish databases, for a total of approximately 78,000 by the end of the study period. Updated estimates in the fifth interim report (2021) indicated that a total of 57,000 empagliflozin initiators were expected to be eligible for inclusion in the study in CPRD-GOLD, Sweden, and Finland by the end 2020. New estimations including the inclusion of CPRD-Aurum and the extension of the study period to the end of 2021 for both CPRD databases suggest that a total of 67,490 empagliflozin initiators could be eligible for inclusion across all three countries. Furthermore, the observed numbers of patients initiating DPP-4 inhibitors in each country suggest that achievable matching ratios would be 1:3 in UK-CPRD, 1:1 in Sweden, and 1:2 in Finland.
 
Power to detect relative risks of 1.5 and 2 was determined at the meta-analysis level, for each of the study outcomes, based on the expected number of individuals exposed to empagliflozin eligible for inclusion in the study for each country (approximately 16,887 in UK-CPRD (GOLD and Aurum), 32,334 in Sweden, and 18,269 in Finland) and the observed IRs of urinary tract cancers, bladder cancer and renal cancer in country-level study populations as reported in the fifth interim report (UK-CPRD: 111.5, 66.7, 26.5 per 100 000 PY; Sweden: 164.5, 104.1, 58.0 per 100 000 PY; Finland: 161.5, 86.8, 71.6 per 100 000 PY; respectively for urinary tract cancer, bladder cancer and renal cancer). Power calculations performed for the primary comparison between empagliflozin users and DPP-4 inhibitors indicated that the power at the meta-analysis level for detecting a hazard ratio of 1.5 would be 93.6% for urinary tract cancer and 84.0% for bladder cancer. Power for detecting a hazard ratio of 2.0 for renal cancer would be 97.0%.
		

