8.9.1 Bias

Potential source of difference in cancer incidence may arise due to channelling bias, detection bias and confounding. The channelling bias is addressed through both two-stage modelling approach wherein individuals are first matched on PS conditional on variables that affect exposure and outcome. Confounding will be minimized through model adjustment after carefully selecting variables using the variable selection criteria. However, there may be confounding due to unobserved variables and/or incomplete adjustment. Detection bias is inherent in cancer studies, especially those where the outcome is based on cancer notification. Although the notification is complete, early stages may go undetected. In studies including exposures with publicized safety concerns, diagnostic bias is also a concern, as patients with the exposure may be more likely to receive screenings for the outcome. The potential for diagnostic bias will be evaluated and addressed through consideration of the frequency of urine dipstick testing (as captured through albuminuria tests) and stage of cancer at the time of diagnosis (as more early-stage cancers in one group would be suggestive of diagnostic bias).

Bias due to definitions of exposure, definition of follow-up times and other relevant covariates will be addressed through sensitivity analyses. As mentioned in [Section 8.9](#), the AT approach used as the primary analysis is subject to omission of cancer cases due to censoring after treatment switch or treatment discontinuation. An ITT approach will therefore be used in sensitivity analyses.

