All continuous variables will be described using standard statistical measures, i.e. range, mean, standard deviation, median, first and third quartile. All categorical variables will be summarized with absolute and relative frequencies. The standardized differences and p-values for the statistical tests will be also reported.

Results will be reported in 4 tables similar to Table 18.

Standardized difference < 10% will be used as indicator of satisfactory distribution balance after matching [8]. Variables with standardized difference larger than 10% might still exist. The unbalanced variables will be considered as potential confounders and included in the adjustment of Cox's PH model, as described in the comparative analysis (Section 6.7.2). In case a substantial amount of variables remain unbalanced, the PS matching procedure will be re-evaluated by, for example, reducing the caliper width.

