Crude incidence rates	Using matched cohorts Country specific analysis (9 tables, 3 outcomes x 3 countries)	As treated exposure definition	Further outcomes- Table 9	Table 29
Hazard ratio estimates using adjusted model	Using matched cohorts (3 tables, 3 outcomes)	As treated exposure definition	Further outcomes- Table 9	Table 25
TNM staging at diagnosis	Using matched cohorts (9 tables, 3 outcomes x 3 countries)	As treated exposure definition	Further outcomes- Table 10	Table 21
Albuminuria tests each year	Using matched cohorts (3 tables, 3 countries)	As treated exposure definition	NA	Table 36
Sensitivity analysis:				
Extended latency period				
Hazard ratio estimates using adjusted model	Using matched cohorts Duration of latency period is extended to 12 months. (3 tables, 1 outcome x 3 countries)	As treated exposure definition	Urinary tract cancer as defined in Table 8	Table 25
Meta-analysis of adjusted HR estimates	Using adjusted HR estimates with 95% CIs from all study countries (1 figure, 1 outcome)	As treated exposure definition	Urinary tract cancer as defined in Table 8	Figure 8
Hazard ratio estimates using adjusted model	Using matched cohorts Discontinuation is 6 months after last day of medication or switch. (3 tables, 1 outcome x 3 countries)	As treated exposure definition	Urinary tract cancer as defined in Table 8	Table 25
Meta-analysis of adjusted HR estimates (discontinuation is 6 months after last day of medication or switch)	Using adjusted HR estimates with 95% CIs from all study countries (1 figure, 1 outcome)	As treated exposure definition	Urinary tract cancer as defined in Table 8	Figure 8

Analysis	Details	Exposure definition	Outcomes	Template
Sensitivity analysis: Inclusion of the Aurum CPRD database				
Description of patient baseline characteristics for the UK, stratified by CPRD database	CPRD specific analysis (1 table)	N/A	N/A	Table 37
Stratified incidence rates	Using UK matched cohorts (3 tables, 3 outcomes x 1 country)	As treated exposure definition	Main outcomes- Table 8	Table 38
Hazard ratio estimates using crude model after adding CPRD database as a stratification variable	Using UK matched cohorts (3 tables, 3 outcomes x 1 country)	As treated exposure definition	Main outcomes- Table 8	Table 39
Hazard ratio estimates using the base model after adding CPRD database as a stratification variable	Using matched cohorts Only for the UK (3 tables, 3 outcomes x 1 table)	As treated exposure definition	Main outcomes- Table 8	Table 40

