Standardized differences for baseline covariates comparing patients using empagliflozin at index date to patients using [drug group] at index date in the unmatched and matched cohorts – [Country] data

Proprietary confidential information © 2024 Boehringer Ingelheim International GmbH or one or more of its affiliated companies

Figure 5 Propensity score distribution in non-matched empagliflozin users at index date, matched empagliflozin users at index and matched DPP-4 inhibitors users at index – [Study country], [Cohort].

Proprietary confidential information © 2024 Boehringer Ingelheim International GmbH or one or more of its affiliated companies

Proprietary confidential information © 2024 Boehringer Ingelheim International GmbH or one or more of its affiliated companies

Table 19 Propensity score distribution before and after propensity score matching of empagliflozin users and DPP-4 inhibitors users by decile in [country]

Propensity score	Decile 1	Decile 2	Decile 3	Decile 4	Decile 5	Decile 6	Decile 7	Decile 8	Decile 9
Before matching									
Empagliflozin users	x.xxx								
DPP-4 inhibitors users	x.xxx								
After matching									
Matched empagliflozin users	x.xxx								
Matched DPP-4 inhibitors users	x.xxx								

Proprietary confidential information © 2024 Boehringer Ingelheim International GmbH or one or more of its affiliated companies

Table 20 Number of patients with incidence of cancer within 12 months after index date

	Empagliflozin users at index date	DPP-4 inhibitors users at index date
Number of cancers within 12 months after index date.	N (x.xx%)	N (x.xx%)

Proprietary confidential information © 2024 Boehringer Ingelheim International GmbH or one or more of its affiliated companies

Table 21 TNM staging of [Study outcome] at diagnosis during follow-up after exclusion of cancers occurring within 6 months after index date.

	[Study outcome] cases in empagliflozin users at index date	[Study outcome] cases in DPP-4 inhibitors users at index date
TNM staging (T)		
T0	N (x.xx%)	N (x.xx%)
T1	N (x.xx%)	N (x.xx%)
T1a	N (x.xx%)	N (x.xx%)
T1b	N (x.xx%)	N (x.xx%)
T1c	N (x.xx%)	N (x.xx%)
T2	N (x.xx%)	N (x.xx%)
T3	N (x.xx%)	N (x.xx%)
T4	N (x.xx%)	N (x.xx%)
TX	N (x.xx%)	N (x.xx%)
NA	N (x.xx%)	N (x.xx%)
TNM staging (N)		
N0	N (x.xx%)	N (x.xx%)
N1	N (x.xx%)	N (x.xx%)
NX	N (x.xx%)	N (x.xx%)
NA	N (x.xx%)	N (x.xx%)
TNM staging (M)		
M0	N (x.xx%)	N (x.xx%)
M1	N (x.xx%)	N (x.xx%)
MX	N (x.xx%)	N (x.xx%)
NA	N (x.xx%)	N (x.xx%)

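### The stage check for diagnostic bias has only per-country counts and percentages listed for it, which say little about whether a raised hazard ratio is harm or extra detection; stage-specific hazard ratios would say more

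*SAP*

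**What the plan says.** SAP 6.3 says diagnostic bias will be examined in sensitivity analyses "through consideration of the frequency of urine dipstick testing" (captured through albuminuria tests) and stage at diagnosis, with the stated rationale "as more early-stage cancers in one group would be suggestive of diagnostic bias". SAP 4.1 and protocol 8.1 reason in the same way, and protocol 8.9.1 repeats that "more early-stage cancers in one group would be suggestive of diagnostic bias".

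SAP Table 16 gives stage one row, "TNM staging at diagnosis", described as "Using matched cohorts (9 tables, 3 outcomes x 3 countries". Its template is Table 21 in Annex III, titled "TNM staging of [Study outcome] at diagnosis during follow-up after exclusion of cancers occurring within 6 months after index date". The template has N (%) for each T, N and M category in each drug group, with rows for unassessed and missing stage. It has no early/advanced grouping, rate, difference, CI or test.

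Other parts of the plan go further. The further outcomes in the same block of Table 16 get HRs. The intention-to-treat, grace-period and latency analyses get both HRs and meta-analysis. For baseline balance, SAP 6.6.2 says "The standardized differences and p-values for the statistical tests will be also reported".

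**The concern.** The protocol itself expects that urinary signs or symptoms may be looked for more often in empagliflozin users. If the urinary tract cancer HR is raised, the first question will be whether that reflects harm or earlier detection, and stage is one of the two checks named for it.

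The listed output cannot carry much of that weight. Read literally, having more early-stage cancers is a count, and counts depend on how many comparators were matched. Read as a percentage of cases, a harm that acts equally on all stages leaves the expected share unchanged, so the observed direction is then close to a coin toss. The quantity least affected by extra screening, the HR for advanced-stage cancer, is not estimated anywhere in the readable plan.

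**Working it through.** **Inputs.**
- Empagliflozin initiators (protocol abstract): "approximately 16,887 in UK-CPRD (GOLD and Aurum), 32,334 in Sweden, and 18,269 in Finland".
- Matching ratios 1:3, 1:1 and 1:2, and mean follow-up 2.4, 2.2 and 2.4 years (protocol 8.5).
- Urinary tract cancer rates 111.5, 164.5 and 161.5 per 100,000 person-years; renal 26.5, 58.0 and 71.6 (protocol 8.5).
- Six-month lag (protocol 8.3.5).

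**Reproducing the plan's figure.** This fixes the case numbers. With r comparators per empagliflozin user and k = 1/r, Freedman's formula is power = Φ(√(D·k)·|HR − 1|/(k·HR + 1) − 1.96), where D = N × t × IR × (HR + r). At HR 1.5 for all urinary tract cancer:

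| | t (years) | D | Power | Protocol Table 7 |
|---|---|---|---|---|
| UK | 1.7 | 144.0 | 63.7% | 63.7% |
| Sweden | 1.7 | 226.1 | 85.2% | 85.1% |
| Finland | 1.9 | 196.2 | 80.8% | 80.6% |

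Sweden and Finland match once the lag is deducted. For the UK, 2.4 − 0.5 = 1.9, but Table 7 is reproduced only at 1.7, so 1.7 is inferred. (With the 16,360 initiators in the Table 7 footnote, 1.7 years gives 62.3%.)

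**Expected cases with no effect.** These are N × t × IR for empagliflozin, times r for DPP-4. Sweden, for example: 32,334 × 1.7 × 164.5/100,000 = 90.4.
- All urinary tract, empagliflozin vs DPP-4: UK 32 vs 96, Sweden 90 vs 90, Finland 56 vs 112. At 1.9 years the UK would be 36 vs 107.
- Renal: 8 vs 23, 32 vs 32, 25 vs 50.

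**Assumptions from here on.** The documents give no early-stage share, so 50–70% is assumed, with every case staged. Early and late counts were simulated as Poisson, 100,000 runs per scenario.

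**Count reading, all urinary tract cancer.** With no effect, empagliflozin has more early-stage cases in at most 2% of UK and Finnish tables and a little under half of Swedish ones. Under a stage-neutral HR of 1.5 it has more in about 98–99% of Swedish tables but at most 7% of UK and Finnish ones. The answer tracks the matching ratio.

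**Share reading.** With no effect and no bias, the empagliflozin share is higher in about 50% of country tables. Under a stage-neutral HR of 1.5 it is still about 50%. An exact binomial calculation with early shares from 30% to 85% gives 43–56% and 47–54%. All three countries point to empagliflozin by chance in roughly 10–12% of runs (0.5³ = 12.5% before ties).

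**Chance variation in a share difference.** With 60% early stage, the 95% half-width is 1.96 × √(0.24 × (1/n₁ + 1/n₀)).
- Urinary tract: UK 20 points, Sweden 14, Finland 16.
- Renal: 24 to 40 points.

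**If only early detection is raised** (early HR 1.5, late HR 1.0). In Sweden with 50% early stage, the empagliflozin share is 67.8/(67.8 + 45.2) = 60% against 50%. The standard error is √(0.24/113 + 0.25/90.4) = 7.0 points, so z = 1.43 and the share is higher about 92% of the time. The direction is therefore sensitive to bias, but it appears about half the time without any.

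**Advanced-stage HR.** At HR 1.5 with half the cases late-stage, expected late cases are UK 24 vs 48, Sweden 67.8 vs 45.2 and Finland 42.1 vs 56.1. The weights 1/(1/e + 1/d) are 16.0, 27.1 and 24.0, summing to 67.1. The pooled standard error is 1/√67.1 = 0.122, a 95% CI factor of exp(1.96 × 0.122) = 1.27. With 30% late-stage the factor is 1.36. Estimating between-country variance by DerSimonian–Laird widens this, to about 1.3–1.5 overall. In the simulation the pooled lower limit exceeds 1 in 63–83% of runs under stage-neutral harm, and in about 2% when only early detection is raised.

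**The case against.** A reader might infer that the SAP contains a rule comparing early-stage shares by sign, that it flags bias falsely half the time, and that it would be used to explain away a real signal. The documents do not support that. The early-stage phrase is a bracketed rationale, says only that a difference would be suggestive, and sits beside test frequency. Neither shares nor a sign-only decision is specified, and no readable text discounts an HR. The half applies to a single country table on one reading; agreement across all three countries by chance is much rarer.

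Absence is also hard to prove here. SAP 6.8–6.9, SAP Table 10 (the outcome definition cited in the staging row) and protocol 8.7.2 are not readable in the public versions. Table 16 is not exhaustive: it has no row for the planned 1:1 matching analysis. Protocol Annex 5 already classes cancer characteristics as a sensitivity or descriptive item. Other features help against detection bias: albuminuria testing is a propensity-score candidate, and the 6- and 12-month lags remove cancers found soon after initiation.

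All of this stands, and it limits the claim to the readable text. It does not supply an estimate that separates harm from detection. Leaving count or share open adds to the problem, because the two readings can give opposite answers in the same country.

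**Conclusion.** The point holds in this form: as listed, the stage comparison is a set of small per-country descriptive tables whose direction says little about whether a raised HR is harm or detection. On a count reading it follows the matching ratio. On a share reading without a CI, it favours either drug about equally by chance in each country, at HR 1 and at a stage-neutral HR of 1.5. It is not shown that the plan would dismiss a raised HR, nor that the unreadable sections lack a better analysis.

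The figures rest on the protocol's expected sizes and rates, an assumed early share and complete staging. The inferred UK follow-up does not change the conclusion. As-treated censoring and missing stage would reduce the case numbers and widen chance differences. This is a worthwhile, inexpensive improvement; it does not invalidate the primary analysis.

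**What to change.** Add rows to SAP Table 16 for as-treated HRs with 95% CIs for early-stage and for advanced-stage urinary tract cancer, and for bladder cancer where events allow. Use the base model, per country and pooled by the planned random-effects method. State in advance which T, N and M categories count as early and advanced, and report unknown stage as its own category.

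Stage is not among the minimum data items in protocol Table 5, and UK cancer registry data were dropped, so a country's staging may prove unusable. In that case give country-level results and label any two-country pooling as a stated exception to protocol 8.7.1.4, which pools only where all three countries have estimates.

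Replace the bracketed wording in SAP 4.1 and 6.3 and protocol 8.1 and 8.9.1 with:

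> Table 21 counts and percentages are descriptive; diagnostic bias is assessed from the early- and advanced-stage HRs with their 95% CIs. A raised advanced-stage HR counts against diagnostic bias; an advanced-stage CI that includes 1 does not by itself show diagnostic bias.

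A yes/no rule that declares bias when the early-stage CI lies above 1 and the advanced-stage CI includes 1 should not be adopted. Under the same assumptions it would label a real stage-neutral HR of 1.5 as bias in about 14–35% of runs.

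Cost: a few more Cox fits and forest plots on stage data already planned for Table 21, and a wording amendment to both documents. The advanced-stage HRs will be imprecise (95% CI factor about 1.3–1.5 for urinary tract cancer, wider with missing stage). No new patients are needed.

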6.4. PROPENSITY SCORE MATCHED COHORTS

Matched full cohort

Propensity score matched cohorts will be derived in each country by matching each initiator of empagliflozin at index date with initiators of DPP-4 inhibitors at index date with a variable matching ratio up to 1:3 (1:1 in a sensitivity analysis) using greedy matching methods (cf. Section 6.5). Free or fixed dose combination use of metformin at index date will be used as an exact matching variable.

Matched metformin-user only cohort

Using the propensity scores computed using the entire cohort, a matched metformin-user only cohort will be derived by matching within a subgroup including only patients using metformin in free or fixed dose combination with the study drugs at index date. Each initiator of empagliflozin at index date will be matched with initiators of DPP-4 inhibitors at index date with a variable matching ratio up to 1:3 using greedy matching methods (cf. Section 6.5).

6.5. IMPLEMENTATION OF THE PROPENSITY SCORE MATCHING

6.5.1. Estimation of the propensity score

Propensity score model specification

The propensity score will be estimated using a binary logistic regression model. For all individuals, propensity scores for the comparison empagliflozin vs. DPP-4 inhibitors will be computed at the index date as the probability to receive empagliflozin, conditional on treatment and clinical history up to index date within each stratum.

The resulting propensity score model will be used to create two matched cohorts in each country:

- Matched full cohort, including patients initiating empagliflozin or a DPP-4 inhibitor at index date.
- Matched metformin-user only cohort, including patients using metformin in free or fixed dose combination with empagliflozin or a DPP-4 inhibitor at index date.

Variables considered for inclusion in the propensity score model

The following variables will be evaluated at index date and considered for inclusion in the propensity score model:

- Demographics and other baseline characteristics at index date Table 11.
- Diabetic complications Table 12 (status at index date).
- Non-diabetic concomitant disease Table 13 (status at index date).
- Diabetic concomitant medication use Table 14 (status at index date).
- Non-diabetic concomitant medication use Table 15 (status at index date).

